## **5.2. Sample size calculation**

Sufficient information to perform a formal sample size calculation is lacking. During a 2-month period all patients meeting the inclusion and exclusion criteria will be recruited. Based on current rates of admissions in the mentioned services, we expect to recruit at least 300 patients (75 patients per operator, 15 for each of the 5 inclusion categories) during a 2 months data collection period.

## **5.3. Study period**

The enrollment period will last two months. Demographic and baseline clinical data are recorded on admission while outcome data are captured at hospital discharge. The hospital discharge of the last patient enrolled will be considered the end of the data collection period for this study. The study period will end at completion of data analysis.

## **6. METHODS**

### **6.1. Study parameters/endpoints**

#### **6.1.1. Main study parameter/endpoint**

The primary endpoint is the mean aggregated diagnostic accuracy between the ultrasound findings collected via hand held devices as compared to the conventional apparatus.

#### **6.1.2. Secondary study parameters/endpoints**

1. Detailed diagnostic accuracy for each of the nine ultrasound findings.
2. Inter-observer agreement on ultrasound findings between naïve and intermediate operators.
3. Mean 'quality of image score' (0-4) for each of the nine ultrasound findings.
4. Proportion of complete ultrasound examinations i.e. with all pre specified findings allocated for the category being completed.

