## 1. PROJECT SUMMARY

**Rationale:** The majority of obstetric emergencies are identified through clinical examination, which cannot be substituted by ultrasound. However, just as a laboratory exam, ultrasonography can provide swift point of care information on fetus presentation, viability, placenta position, quantity of amniotic fluid and presence of abdominal fluid to inform the clinical reasoning and therapeutic escalation. Ultrasound literature in low-resource settings has favoured antenatal care (ANC) rather than the emergency setting. Also, hand-held ultrasound machines may not be as performant as traditional machines used by expert operators but to date is still to be tested in a low resource setting.

**Objective:** to assess the *reliability* of **ultrasound findings** measured by hand held ultrasound probes used by operators with variable experience in a low resource hospital.

**Hypothesis:** There is substantial agreement between simple ultrasound findings identified using hand held ultrasound devices and the reference standard.

**Study design:** a prospective observational diagnostic accuracy study.

**Study population:** parturients admitted to the Princess Christian Maternity Hospital (PCMH) in Freetown, Sierra Leone.

**Sample size:** no formal sample size calculation is performed. Based on current rates of admissions to the PCMH we expect to perform obstetrical ultrasound scan in at least 300 patients during a 2–months study period.

**Methods:** 4 trained physicians (3 naive and 1 intermediate ultrasound users) will perform the ultrasound investigations using the hand held device and complete a structured predefined report form of obstetric ultrasound findings at patient admission or according to clinical indications after admission. These will be compared with the reference standard, i.e. an ultrasound examination performed by a specialist gynecologist/obstetrician using a conventional apparatus in the hospital ultrasound room.

**Main study parameters/primary endpoints:** The mean diagnostic accuracy among nine ultrasound obstetric findings collected with hand held devices versus the reference standard.

**Nature and extent of the burden and risks associated with participation, benefit and group relatedness:** Ultrasound is a non–invasive and painless procedure without additional risks.

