### **3.4. Current challenges with obstetric diagnostics in PCMH**

Princess Christian Maternal Hospital (PCMH) is only the tertiary perinatal hospital in Freetown, Sierra Leone, which accommodates nearly 9000 admissions a year (11). More than 6000 deliveries a year are managed at the hospital, with more than one third of cases being major obstetrical emergencies including eclampsia and peripartum hemorrhages. Furthermore, the hospital accepts emergency referrals from 6 hospitals and 112 peripheral clinics in the Western region of the country. Major causes of maternal mortality at PCMH include postpartum and antepartum hemorrhage, eclampsia and infection (12).

In the 2017 Annual Report (12), it was shown that diagnoses made at admission by house doctors at outpatient department were frequently different from the final diagnoses made by the house officers specialized in obstetrics. For example, approximately 40% of the patients admitted to the hospital were initially diagnosed with anemia, but most of them were subsequently found to be in fatal conditions caused by placenta abruption (12). It is obvious that confirming a diagnosis is not the

only step needed to avoid mortality, but it is pivotal to establish a functional system to save critically ill patients. Lack of access to ultrasound in the delivery room often resulted in late diagnosis of malpresentation, breech presentation or multiple pregnancies. Intra-uterine fetal death (IUFD) was frequently observed but unnoticed until they were delivered by unnecessary cesarean sections.

At the emergency outpatient department of PCMH, clinical examinations and history taking are the only means to reach diagnoses, based on which subsequent management strategies are planned. Measurement of hemoglobin and lactate are the only modality available for in-house doctors to support their diagnosis. Ultrasound machine is intermittently available but the frequent low quality of the images acquired and the unstable electric supply of the hospital hampers repeatability and reliability of the ultrasound examinations.

Stethoscope or doppler devices are seldom available or functional. Traube's monaural stethoscope is the only the device available for the in-house doctors or midwives to listen to the fetal heart. Prompt diagnosis and treatment decisions are frequently required in the case of obstetric emergencies, in which delay in the recognition of the conditions of the fetus and mothers often resulted in demise of both.

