##### **5.1.2.Exclusion criteria**

The following exclusion criteria will apply in the observational study:

- Ultrasound examination not feasible, e.g., due to electricity breakdown, or physical absence or unavailability of the trained sonographers.

**Table 1.** Inclusion categories as defined by National Protocols and Guidelines for Emergency Obstetric and Newborn care (14) or hospital protocol.

Inclusion criteria	Case Definition
Vaginal bleeding in early pregnancy	Vaginal bleeding or cramping, with amenorrhea or positive pregnancy test <22 weeks of gestation
Pre-eclampsia	Blood pressure $\geq 140/90$ (at least 2 recordings, 4 hours apart) PLUS any of: proteinuria (at least 2+ on dipstick, headache, generalized oedema, visual disturbance).
APH third trimester:	Vaginal bleeding after 22 weeks of pregnancy or in labour before giving birth. May have final diagnosis of abruptio placentae, placenta previa and ruptured uterus.
Prolonged/ Obstructed labour:	Prolonged latent or active phase, cephalopelvic disproportion, obstructed labor, inadequate uterine activity, prolonged expulsive phase.
High risk pregnancy in ANC	Fulfil any of the following criteria (as defined by hospital protocol): 
 
1. Previous Cesarean Section
 
2. Previous still birth
 
3. Age below 18 years
 
4. Short stature (height < 150cm)
 
5. Grand Multipara: Gravida more than 5.
 
6. Fundal Height >40cm
 
7. Suspected breech
 

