### **6.3. Study procedures**

#### **6.3.1. Training of operators**

The ultrasound operators will receive a 2-week training course. The 1st week training consists of lectures on basic science of ultrasound and tomography, demonstrations by an expert obstetrics sonographer, and hands-on practice at the scanning room of PCMH. The second week of training will focus on how to operate the hand-held ultrasound device, training on the standard operating procedure (SOP) and case report form (CRF) completion.

**Table 2. Ultrasound findings.** Abbreviations: GA, gestational age; FH, fetal heart; MVP, maximum vertical pocket, APH, antepartum hemorrhage; ANC, antenatal clinic.

	Inclusion category	Finding 1	Finding 2	Finding 3	Finding 4
1	Vaginal bleeding in early pregnancy	Intra-uterine pregnancy: yes/no	FH: yes/no	Free fluid in abdomen: yes/no	None
2	Pre-eclampsia	FH: yes/no	Amniotic fluid MVP<2cm: yes/no	GA: ≤34 or >35 weeks	Cephalic presentation: yes/no
3	APH in third trimester	Placenta low lying: yes/no	FH: yes/no	Retroplacental hematoma: yes/no	Amniotic Fluid MVP<2cm: yes/no
4	Prolonged/ obstructed labor	FH: yes/no	Multiple pregnancy: yes/no	Cephalic presentation: yes/no	Amniotic Fluid MVP<2cm: yes/no
5	ANC High Risk Pregnancy*	Cephalic presentation: yes/no	Multiple pregnancy: yes/no	FH: yes/no	Amniotic Fluid MVP<2cm: yes/no
				Placenta low lying: yes/no	GA: ≤34 or >35 weeks

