## **7.2. Statistical analysis**

Data will be reported as mean and standard deviation or median with interquartile range (continuous data), and as frequency and percentage (categorical data). The agreement between the hand-held device and the conventional apparatus on categorical findings scoring will be assessed using diagnostic accuracy and Cohen's K statistics. When appropriate, comparison between subgroups will be performed using Student's t test, ANOVA, Mann-Whitney test or Kruskal-Wallis test for continuous data, and with Chi-square test or Fisher's test for categorical data. A p-value less than 0.05 will be considered statistically significant. Statistical analyses will be performed using R (R Foundation for Statistical Computing, Vienna, Austria). The sensitivity, specificity, positive predictive value, and negative predictive value for each dichotomous ultrasound finding acquired with hand held devices against the reference diagnoses with conventional apparatus will be assessed when appropriate. Quality of images will be assessed by standardized scoring system from 0 to 4 (0= no meaningful images; 1 = poor, not sufficient for interpretation; 2 = good, acceptable for interpretation; 3= excellent, minor suggestions for interpretations; 4 = outstanding, no suggestions for interpretations). All analyses will be conducted after the end of patient recruitment and no interim analyses are planned.

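### One pooled fetal-heart row mixes an absent intra-uterine pregnancy with fetal death, which can raise its specificity and kappa and dilute missed later deaths

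*Protocol*

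**What the plan says.** The summary (section 1) defines the primary endpoint as "The mean diagnostic accuracy among nine ultrasound obstetric findings collected with hand held devices versus the reference standard". The first secondary endpoint in section 6.1.2 is "Detailed diagnostic accuracy for each of the nine ultrasound findings". Section 7.2 adds accuracy, Cohen's kappa and, when appropriate, "The sensitivity, specificity, positive predictive value, and negative predictive value for each dichotomous ultrasound finding acquired with hand held devices".

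Table 2 (section 6.3.1) lists FH as a yes/no finding in every category. In category 1 it stands beside "Intra-uterine pregnancy: yes/no", and no text makes the FH reading depend on that answer. Table 1 (section 5.1.2) defines category 1 as "Vaginal bleeding or cramping, with amenorrhea or positive pregnancy test <22 weeks of gestation", so an IUP is not an entry condition. The completeness endpoint in section 6.1.2 is "Proportion of complete ultrasound examinations i.e. with all pre specified findings allocated for the category being completed"; no not-applicable code is described.

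Section 3.4 gives part of the motivation: "Intra-uterine fetal death (IUFD) was frequently observed but unnoticed until they were delivered by unnecessary cesarean sections".

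**The concern.** In the FH row, specificity is the share of absent hearts that the hand-held scan recognises. The women in that denominator are of different kinds. In a woman with no IUP, an absent heart follows almost automatically once the uterus is read as empty, so both scans will nearly always agree. In categories 2–5 an absent heart is a fetal death, the event that section 3.4 says goes unnoticed.

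Section 4.1.4 itself places intrauterine pregnancy among the easier findings and fetal heart among the more complex ones. In women without an IUP the easier finding largely decides the harder one.

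At stake is what the FH row can support. Someone who wants to know whether the device detects fetal death would look there, and a good pooled specificity or kappa could come largely from early-bleeding women with no IUP.

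**Working it through.** **1. Count of findings.** The cells in Table 2 are: IUP 1, FH 5, free fluid 1, amniotic fluid 4, gestational age 2, cephalic presentation 3, low-lying placenta 2, retroplacental hematoma 1, multiple pregnancy 2. That is 21 cells and nine distinct findings. The plan's count of nine is reproduced only with FH taken as one finding over five categories.

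**2. Sample.** Section 5.2: "we expect to recruit at least 300 patients (75 patients per operator, 15 for each of the 5 inclusion categories". So 5 × 15 = 75 per operator, 4 × 75 = 300 in all, and 300 / 5 = 60 per category. There is no power figure to reproduce.

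**3. Assumed inputs (none is in the protocol).** 40% of early-bleeding women have no IUP; 25% of early IUPs have no FH; fetal death is 6.25% in categories 2–5; half of those deaths are missed; 2% of live later pregnancies are falsely read as absent; FH accuracy in early IUPs is 85%; both scans read absent in every woman without an IUP.

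**4. Expected tables** (positive = heart present).
- Categories 2–5: 240 × 0.0625 = 15 deaths and 225 live. TP = 225 × 0.98 = 220.5, FN = 4.5, TN = FP = 7.5.
- Early IUPs: 60 × 0.60 = 36, of which 27 have FH and 9 do not. TP = 22.95, FN = 4.05, TN = 7.65, FP = 1.35.
- No IUP: 60 × 0.40 = 24, all TN.

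**5. Formulas.** Specificity = TN / (TN + FP). Accuracy p = (TP + TN) / N. Kappa = (p − e) / (1 − e), with e the agreement expected by chance from the margins.

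| FH row | N | TP / FN / TN / FP | Accuracy | Specificity | Kappa |
|---|---|---|---|---|---|
| Categories 2–5 | 240 | 220.5 / 4.5 / 7.5 / 7.5 | 0.950 | 0.50 | 0.53 |
| All women with an IUP | 276 | 243.45 / 8.55 / 15.15 / 8.85 | 0.937 | 0.63 | 0.60 |
| Pooled, all 300 | 300 | 243.45 / 8.55 / 39.15 / 8.85 | 0.942 | 0.82 | 0.78 |

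For the pooled row, e = (252 × 252.3 + 48 × 47.7) / 300² = 0.732, so kappa = (0.942 − 0.732) / (1 − 0.732) = 0.78.

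**6. Attribution.** The 24 women without an IUP account for the step from the second row to the third: +0.18 in specificity and in kappa. The step from the first row to the second comes from genuine readings in early IUPs. Of the 48 absent hearts in the pooled row, 24 are women with no IUP and 15 are fetal deaths.

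**7. Effect on accuracy.** From 93.7% to 94.2% is about 0.5 point on FH, and 0.5 / 9 ≈ 0.06 point on the nine-finding mean.

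**8. Range.** A second set of assumptions uses FH sensitivity 0.95, one true specificity for all women with an IUP, full agreement in women without one, and 300 women in all:

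| Absent-heart rate in IUPs | True specificity | No IUP, n | Specificity, IUP only → pooled | Kappa, IUP only → pooled |
|---|---|---|---|---|
| 5% | 0.50 | 30 | 0.50 → 0.84 | 0.37 → 0.75 |
| 10% | 0.70 | 15 | 0.70 → 0.80 | 0.61 → 0.72 |
| 20% | 0.90 | 6 | 0.90 → 0.91 | 0.82 → 0.83 |

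**9. Dependence on agreement in women without an IUP.** In the scenario of step 4, if 90% rather than all of the 24 agree, TN = 36.75 and FP = 11.25; pooled specificity is 36.75 / 48 = 0.77 and kappa 0.75. In the middle row of step 8, agreement of only 50% lowers specificity from 0.70 to 0.63 and kappa from 0.61 to 0.60. With 90% agreement and a true specificity of 0.90, specificity does not move, although kappa can still rise (0.74 to 0.79 at a 10% absent-heart rate and 15 women).

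**The case against.** Counting FH once names a finding; it does not forbid reporting it by category. Section 7.2 allows subgroup comparisons when appropriate, and a SAP, SOP or CRF not shown here may set denominators and a not-applicable code. This stands in part: nothing prevents separate reporting. But the fixed list of nine, the per-finding measures and the completeness endpoint all point to one FH row, and the generic subgroup wording does not separate the two meanings.

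No endpoint or hypothesis concerns fetal death as such, and a correct absent reading in an empty uterus is a correct reading in the intended population. That stands, and it is why the pooled row should stay.

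Restricting category 1 to women with an IUP would also drop hand-held readings of a heart where the reference finds no IUP, which are real device errors. That stands, and it limits the restriction to a sensitivity analysis.

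Three stronger readings are tempting and are not supported:
- A reader might infer that agreement in women without an IUP is forced. It is near-automatic only: an operator can misread, and absence of an IUP does not strictly exclude cardiac activity elsewhere.
- A reader might infer that missed deaths are hidden. All 7.5 missed deaths in the scenario remain among the 8.85 pooled errors; they are diluted in a rate.
- A reader might attribute the whole distance from 0.50 to 0.82 to women without an IUP. They explain 0.63 to 0.82.

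**Conclusion.** The point holds as a matter of interpretation and reporting. As written, the plan leads to one FH row that mixes absent pregnancy with fetal death, and nothing in the protocol separates them. Specificity is raised if agreement in women without an IUP exceeds the device's true specificity for fetal death; kappa then generally rises too. The illustrative gain of about 0.18 in each rests wholly on assumed rates. Over the second set of assumptions it runs from 0.01 to 0.35 for specificity and from 0.01 to 0.38 for kappa, and it can vanish or reverse if agreement in women without an IUP is poor. A high fetal death rate, which section 3.4 may suggest, makes it smaller.

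A reader might infer that the primary endpoint is biased. It is not, to any useful degree: the nine-finding mean moves by about 0.06 point in the scenario. A diluted contrast between naïve and intermediate operators on FH is plausible but was not calculated, so no claim is made about it.

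**What to change.** In sections 6.1.2(1) and 7.2:
1. Report FH accuracy, sensitivity, specificity and kappa separately for category 1 and for categories 2–5, alongside the pooled row.
2. Base any statement about detecting fetal death on categories 2–5.
3. As a sensitivity analysis, show category 1 FH restricted to women whose reference scan confirms an IUP. Still count and report hand-held readings of a heart in women without an IUP.

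This changes analysis wording only, since Table 2 already has IUP and FH recorded for category 1. The cost is smaller denominators (240 for categories 2–5 and 60 for category 1; 36 for category 1 restricted to IUPs under the assumptions above), wider intervals because fetal deaths may be few, and possibly a less favourable FH kappa.

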#### **4.1.2. Secondary Objectives**

1. To assess the reliability for each pre-defined ultrasound finding.
2. To ascertain if the reliability varies between naïve and intermediate operators.

3. To establish the feasibility of examinations and quality of images acquired with the hand held apparatus.

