### 6.3.2. Ultrasound procedure

Eligible patients will receive:

- a structured point of care ultrasound examination immediately at admission in emergency (or at the point of visit in ANC or ward) by the medical officer using the hand held device and following a simple checklist (Table1).
- the ultrasound examination will be repeated by an expert operator using a standard ultrasound machine in the scanner room of PCMH.

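### Secondary endpoint 2 names inter-observer agreement between naive and intermediate operators, but the protocol plans no paired readings and the endpoint does not match objective 2

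*Protocol*

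**What the plan says.** - **Endpoint.** Section 6.1.2, item 2: "Inter-observer agreement on ultrasound findings between" naive and intermediate operators.
- **Operators.** Section 1: "4 trained physicians (3 naive and 1 intermediate ultrasound users) will perform the ultrasound investigations using the hand held device".
- **Expected numbers.** Section 5.2: "we expect to recruit at least 300 patients", broken down as "75 patients per operator, 15 for each of the 5 inclusion categories".
- **Procedure.** Under section 6.3.2 an eligible patient receives "a structured point of care ultrasound examination immediately at admission in emergency (or at the point of visit in ANC or ward", done by the medical officer with the hand-held device. An expert then repeats the examination on a standard machine in the scanning room.
- **Objective and hypothesis.** Section 4.1.2, item 2: "To ascertain if the reliability varies between" the two operator types. Section 4.1.4, item 2 expects their diagnostic performance to differ only for the more complex findings.
- **Analysis.** Section 7.2 specifies agreement between the hand-held device and the conventional apparatus (diagnostic accuracy and Cohen's kappa), plus comparisons between subgroups. It names no agreement analysis between hand-held operators.
- **Other readings.** Section 7.3 has 20 examinations, 5 per operator, re-read offline by an independent expert.
- **Blinding.** Section 6.1.4 covers the hand-held and reference operators with respect to each other, and not one hand-held operator with respect to another.

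**The concern.** Inter-observer agreement is a paired quantity. To cross-tabulate a naive operator's result against the intermediate operator's, both must have assessed the same patient or the same images. The protocol describes no step that produces such a pair.

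The endpoint also differs in kind from the objective it should serve. Two operators can each agree well with the reference and still never have been compared with each other on one patient. Conversely, two operators can agree closely with each other and both be wrong. Objective 2 and hypothesis 2 concern agreement with the reference. Endpoint 2 concerns agreement between operators.

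Left as it is, a prespecified secondary endpoint either goes unreported for lack of data, or is filled with a comparison across different patients under the name of inter-observer agreement. In the second case the report would claim a property that was never measured. An SAP can choose the statistic, but it cannot supply paired readings that the data collection did not generate.

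**Working it through.** **1. Reproducing the plan's figure.** Inputs: 4 operators (section 1), 5 categories and 15 patients per category (section 5.2).

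- Per operator: 5 × 15 = 75, as stated.
- Total: 4 × 75 = 300, as stated.

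**2. Planned overlap.** Patients with two hand-held scans = sum of operator caseloads − number of patients = 300 − 300 = 0. The section 7.3 re-reads add 4 × 5 = 20 second readings, but each pairs a study operator with an outside expert, so they give 0 naive–intermediate pairs.

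**3. What the design yields instead.** Two separate groups, each compared with the reference: 3 × 75 = 225 naive and 1 × 75 = 75 intermediate patients. Table 2 (section 6.3.1) collects each finding only in certain categories. At 15 patients per operator and category the expected numbers are:

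| Finding | Categories | Intermediate | Naive |
|---|---|---|---|
| Fetal heart | 5 | 75 | 225 |
| Amniotic fluid | 4 | 60 | 180 |
| Cephalic presentation | 3 | 45 | 135 |
| Gestational age | 2 | 30 | 90 |
| Multiple pregnancy | 2 | 30 | 90 |
| Low-lying placenta | 2 | 30 | 90 |
| Intrauterine pregnancy | 1 | 15 | 45 |
| Free abdominal fluid | 1 | 15 | 45 |
| Retroplacental hematoma | 1 | 15 | 45 |

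The last three findings occur in a single category, so there is nothing to adjust for by category. Their sensitivity would rest only on the reference-positive patients among the intermediate operator's 15.

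**4. Precision of the unpaired comparison.** The protocol gives no accuracies. Assume 0.90 to 0.95 for the intermediate operator and 0.80 to 0.85 for the naive operators. The 95% half-width for the difference is 1.96 × √[p₁(1−p₁)/n₁ + p₂(1−p₂)/n₂].

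- 75 vs 225, p₁ = 0.95, p₂ = 0.85: 1.96 × √(0.000633 + 0.000567) = 0.068.
- 75 vs 225, p₁ = 0.90, p₂ = 0.80: 1.96 × √(0.001200 + 0.000711) = 0.086.
- 15 vs 45: both are larger by √5, giving 0.152 and 0.192.

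This treats patients as independent and ignores variation among the three naive operators.

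**The case against.** **One scan per patient is inferred.** The protocol never says that each patient has only one hand-held operator. Section 5.2 gives an expected recruitment, not an allocation rule, and section 6.3.2 does not forbid a second scan. This stands as a limit on wording: the disjoint caseloads are a strong inference from a single described scan and from 4 × 75 = 300. A minimum of 300 allows more patients but does not plan any overlap, and no section provides for a second hand-held scan.

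**Impossible, or only unplanned?** A reader might infer that the endpoint can never be computed. The documents do not support that. Section 7.3 already envisages offline reading, and the device description in the appendix (2.1) mentions image recording. Naive and intermediate operators could in principle cross-read stored images. The protocol does not plan this, and it would measure interpretation without acquisition. So the endpoint is unsupported as written, which is less than impossible.

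**Loose wording.** Objective 2, hypothesis 2 and section 7.2 all point to a comparison against the reference, so the endpoint may simply be mislabeled. That is plausible. It lowers the severity and points to the remedy, but the label still names a different quantity and should not reach the report.

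**Conclusion.** The point holds as an inconsistency inside the protocol. Endpoint 2 requires naive–intermediate pairs, and the described procedures plan 0 among the 300 expected patients. The endpoint also does not correspond to objective 2, hypothesis 2 or the agreement analysis in section 7.2. The zero rests on reading section 6.3.2 as one hand-held scan per patient, which the arithmetic of section 5.2 supports and nothing in the protocol contradicts.

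A reader might go further and conclude that the question of operator experience is lost, or that the main result is compromised. Neither follows. The primary endpoint compares hand-held with conventional findings and needs no operator pairs. Objective 2 can be addressed with about 225 naive and 75 intermediate patients, if caseloads and category numbers turn out as expected. Under the assumed accuracies, the half-width for a difference is about 7 to 9 percentage points for fetal heart and 15 to 19 for findings collected in one category. Severity: should be fixed.

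**What to change.** Replace item 2 of section 6.1.2 with: *Difference between naive and intermediate operators in agreement with the reference standard (diagnostic accuracy and kappa; sensitivity and specificity where numbers allow), per finding, with 95% CI.* Adjust for inclusion category only for the six findings collected in more than one category. Do not call the result inter-observer agreement.

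Add one sentence on the limits: the comparison is unpaired and non-randomized (section 6.1.4) and rests on one intermediate operator, so experience cannot be separated from that individual or from case mix.

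Cost: one reworded line and one added sentence, with no extra scans or staff. What is given up is any statement on agreement between hand-held operators.

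If the investigators do want that statement, a blinded second hand-held scan or a cross-reading of stored images in a defined subset has to be planned before enrolment. As an illustration, having a naive operator rescan the intermediate operator's 75 patients costs 75 extra scans and gives 75 pairs. With SE(κ) = √{(1−κ)/n × [(1−κ)(1−2κ) + κ(2−κ)/(2p(1−p))]} and assumed κ of 0.6 to 0.8 and prevalence p of 10% to 50%, the 95% half-width at n = 75 runs from 0.14 (κ = 0.8, p = 50%) to 0.31 (κ = 0.6, p = 10%). Only fetal heart would have all 75 pairs. Findings collected in fewer categories would have fewer pairs and wider intervals.
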